7.2. Determination of Sample Size

For methods related to determination of sample size, refer to specific sub-protocols. Additional patients will be enrolled to account for any patients who are lost to follow-up or have no follow-up imaging.

7.3. Statistical Methods

The SAP will be produced individually for each sub-protocol prior to analysis.

7.3.1. Efficacy Analyses

The efficacy analyses will be performed on the full analysis set (FAS) population which includes all patients who received at least 1 dose of study drug and have measurable disease as determined by the Investigator at baseline and have at least 1 follow-up imaging or radiographically confirmed progressive disease prior to the first imaging timepoint.

ORR as assessed by the proportion of patients with the best overall confirmed response of CR or PR, according to the appropriate tumor response criteria as assessed by Investigator will be calculated and an exact CI will be calculated. DOR in patients with best overall response of CR or PR as determined by the treating Investigator defined as from time of first tumor response to progression or date of data analysis, whichever occurs earlier will be calculated. PFS is defined as the time from the date of the first dose of study drugs to the first occurrence of disease progression according to the appropriate tumor response criteria as

assessed by Investigator, or death from any cause, whichever occurs earlier. OS is defined as the period from the date of the first dose of study drugs until the date of death from any cause. Kaplan-Meier curves will be plotted for DOR, PFS, and OS. TTR in patients with best overall response of CR or PR will be determined by the treating Investigator from the initiation of study treatment to the date of first response. The timepoint for the analysis of response for Phase 2 studies' primary efficacy objective will be when all patients have a minimum of 6 months of follow-up.

7.3.2. Safety Analyses

Safety will be assessed by clinical review of all relevant parameters, including AEs, SAEs, AESIs, laboratory values, and vital signs. Unless specified otherwise, the safety analyses will be conducted for the Safety Analysis Set defined in Section 7.1.

The reported AE term will be assigned a standardized Preferred Term using the Medical Dictionary for Regulatory Activities (MedDRA), version 24.0 or later, and adverse event severity will be graded according to National Cancer Institute (NCI) CTCAE v5.0.

Treatment-emergent adverse events will be tabulated according to MedDRA by system organ class, high level terms, and preferred terms and will be include the following categories: frequency of AEs overall, by grade, relationship to study treatment, time-of-onset, duration of the event, duration of resolution, and any concomitant medications administered. A listing of TEAEs resulting in study drug discontinuation will be provided. For reporting purpose, treatment-emergent adverse event is defined as new or worsening adverse events occurring on or after the first dose of study drug is administered until the clinical cutoff date. All safety analyses of adverse events will also include all adverse events with onset on or after the first study drug treatment until the data cutoff date.

7.3.2.1. Deaths

All deaths on study should be reported and recorded. Deaths will be reported in a patient listing and will include the primary cause of death and the number of days between the date of the last dose of study drug and death.

7.3.2.2. Laboratory Values

Laboratory values will be assigned toxicity grades when available using the NCI CTCAE, version 5.0 or later. Directional shifts in laboratory toxicity grades (comparing baseline grade with worst post-baseline grade) will be analyzed using standard shift tables, presenting number and proportion of patients and their maximum grade shift. For analytes without a toxicity grading scale, the shift table will present directional shifts from baseline to above or below the laboratory standard normal range using the maximum increase and/or decrease observed throughout the course of treatment/observation. Descriptive statistics for the actual values of clinical laboratory parameters (and/or change from baseline in clinical laboratory parameters) and other safety parameters as deemed appropriate will be presented for all scheduled measurements over time. Mean laboratory values over time will be presented for key laboratory parameters.

7.3.2.3. Vital Signs

All patients will have pretreatment baseline vital signs and pre-dose measurements as described in the Schedule of Activities in the relevant sub-protocol. The results for each vital sign will be summarized in a descriptive manner by calculating the mean, standard deviation, median, and range by time point in the same manner described for laboratory values. For these analyses, the minimum, maximum, average, and last post-baseline value will be determined relative to the baseline vital sign measurements only.

7.3.2.4. Concomitant Medications

Prior and concomitant medications will be coded to the generic term using the current version of the World Health Organization (WHO) Drug Dictionary and listed by patient.

7.3.3. Pharmacokinetic Analyses

Plasma concentrations of DAY101 and other therapies (as applicable based on sub-protocol) will be determined with validated bioanalytical methods. Plasma concentrations will be analyzed at specified time points in order to generate PK parameters as appropriate and will be described in more detail in the sub-protocol(s). Summary statistics will be generated as appropriate.

8. ADVERSE EVENTS

8.1. Adverse Events, Adverse Events of Special Interest, and Serious Adverse Events

Adverse events will be reported by the patient (or, when appropriate, by a caregiver, surrogate, or the patient's legally authorized representative).

The Investigator and any qualified designees are responsible for detecting, documenting, and recording events that meet the definition of an AE, AESI, or SAE and remain responsible for following up AEs that are serious, considered events of special interest, considered related to the study intervention or study procedures, or caused the patient to discontinue DAY101 or combination partner.

All AEs, whether reported by the patient or the patient's parent/legal guardian or noted by study personnel, will be recorded in the patient's medical record on the Adverse Event eCRF.

See Appendix G for instructions on collection, assessing, and reporting of AEs.

8.1.1. Time Period and Frequency for Collecting Adverse Event, Adverse Events of Special Interest, and Serious Adverse Event Information

Report all SAEs deemed related to protocol-mandated procedures from the signing of informed consent through to start of treatment with DAY101 or combination partner, whichever is administered first.

Report all AEs, AESIs, including SAEs, from the start of treatment until 30 days after the last dose of DAY101 or combination partner, whichever was administered last.

For patients who screen fail or are enrolled but do not receive study drug, the reporting period for SAEs ends 30 days after the last procedure (e.g., screening procedure).

Table 8: Summary of AE Collection Periods

Time Period	AE Collection
ICF signature to start of study drug	Protocol/procedure-related SAEs only
Start of study drug to 30 days after last study drug dose (DAY101, additional study treatment, whichever was administered last) ^a	All AEs, AESIs, and SAEs
Beyond 30 days after last study drug dose (DAY101, additional study treatment, whichever was administered last)	Any SAEs or AESIs related to study drug

Abbreviations: AE, adverse event; AESI, adverse event of special interest; ICF, informed consent form; SAE, serious adverse event.

^a See Section 8.1.3 for follow-up of AEs. If a patient begins a new anticancer therapy, the AE reporting period for non-SAEs and SAE/AESIs not related to study drug ends at the time the new treatment is started.

Report and record all SAEs to the Sponsor or designee within 24 hours following the Investigator's knowledge of the events, as indicated in Appendix G. The Investigator will submit any updated SAE data to the Sponsor within 24 hours of their being available.

Non-serious AESIs should be reported in the same manner as reporting of SAEs. In addition, for both serious and non-serious AESIs, the appropriate targeted questionnaires should be submitted to the Sponsor with the SAE report or as soon as possible.

If the Investigator learns of any SAE and/or AESI, including a death, at any time after a patient has been discharged from the study, and he/she considers the event to be reasonably related to the study intervention or study participation, the Investigator must promptly notify the Sponsor.

8.1.2. Method of Detecting Adverse Events, Adverse Events of Special Interests, and Serious Adverse Events

The method of recording, evaluating, and assessing causality of AEs, AESIs, and SAEs and the procedures for completing and transmitting SAE and non-serious AESI reports are provided in Appendix G.

Care will be taken not to introduce bias when detecting AEs, AESIs, and/or SAEs. Open-ended and nonleading verbal questioning of the patient or the patient's parent/legal guardian is the preferred method to inquire about AE occurrences.

8.1.3. Follow-up of Adverse Events, Adverse Events of Special Interests, and Serious Adverse Events

After the initial AE/SAE report, the Investigator is required to proactively follow each patient at subsequent visits/contacts. All SAEs will be followed until resolution, stabilization, the event is otherwise explained, or the patient is lost to follow-up. Further information on follow-up procedures is provided in Appendix G.

Non-serious AESIs should be followed-up in the same manner as SAEs.

If a patient begins a new anticancer therapy prior to 30 days post study drug EOT, the AE reporting period for non-SAEs and SAE/AESIs not related to study drug ends at the time the new treatment is started.

8.1.4. Regulatory Reporting Requirements for Any SAEs and Non-Serious AESIs Occurring During this Study Must Be Reported as Follows:

- Prompt notification of an SAE or AESI by the Investigator to the Sponsor is essential so that legal obligations and ethical responsibilities toward the safety of patients and the safety of a study intervention under clinical investigation are met. Any SAEs (including Serious AESIs) must be reported to the Sponsor via email at [REDACTED] within 24 hours. Non-serious AESI's should be reported using the same processes and timelines as SAEs.
- The Sponsor has a legal responsibility to notify both the local regulatory authority and other regulatory agencies about the safety of a study intervention under clinical investigation. The Sponsor will comply with country-specific regulatory requirements relating to safety reporting to the regulatory authority, Institutional Review Boards (IRB)/Independent Ethics Committees (IEC), and Investigators.

- An Investigator who receives an Investigator safety report describing an SAE or other specific safety information (e.g., summary or listing of SAEs) from the Sponsor will review and then file it along with the IB and will notify the IRB/IEC, if appropriate, according to local requirements. A non-serious AESI does not require expedited reporting to any regulatory health authority or agency.

8.1.5. Pregnancy or Combination Partner

There is no relevant clinical experience with DAY101 (as a single agent or in combination) in pregnant or lactating female patients, and animal reproductive studies have not been performed. Women of childbearing potential must have a negative pregnancy test prior to enrollment because of the potentially dangerous effects of the preparative chemotherapy on the fetus. This experimental therapy should not be administered to pregnant women or women who are breastfeeding.

- Details of all pregnancies in female patients and female partners of male patients will be collected for pregnancies occurring after the start of study intervention until 6 months after completing DAY101.
- If a pregnancy is reported, the Investigator should inform the Sponsor within 24 hours of learning of the pregnancy and should follow the procedures outlined in Appendix F.
- If a lactation case is reported, the Investigator should inform the Sponsor within 24 hours of learning of the lactation case and should follow the procedures outlined in Appendix F.
- Abnormal pregnancy outcomes (e.g., spontaneous abortion, fetal death, stillbirth, congenital anomalies, ectopic pregnancy) are considered SAEs.

In addition to reporting any pregnancies or lactation cases occurring during the study, Investigators should monitor for pregnancies or lactation cases that occur after the last dose of DAY101 through 6 months for female patients and for 6 months for female partners of male patients.

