Appendix E: List of Research Uses of Tissue, Plasma and Clinical Data

Appendix F: Contraceptive Guidance and Collection of Pregnancy Information

Definitions:

Woman of Childbearing Potential (WOCBP)

A woman is considered to be fertile following menarche and until becoming postmenopausal, unless permanently sterile (see below).

If fertility is unclear (e.g., amenorrhea in adolescents or athletes) and a menstrual cycle cannot be confirmed before first dose of study intervention, additional evaluation should be considered.

Women in the following categories are not considered WOCBPs:

- Premenarchal
- Premenopausal woman with one of the following:
 - Documented hysterectomy
 - Documented bilateral salpingectomy
 - Documented bilateral oophorectomy
 - For individuals with permanent infertility due to an alternate medical cause other than the above (e.g., Müllerian agenesis, androgen insensitivity), Investigator discretion should be applied to determining study entry.

Note: Documentation can come from the site personnel's review of the patient's medical records, medical examination, or medical history interview.

Contraception Guidance:

Male patients are not allowed to donate sperm during the course of this study or within 180 days after receiving their last dose of study drug.

Female and male patient of reproductive potential must agree to avoid becoming pregnant or impregnating a partner, respectively, while receiving study drug(s) and for 180 days after the last dose of study drug(s) by complying with one of the following:

(1) practice abstinence† from heterosexual activity;

OR

(2) use two acceptable methods of contraception in which one method must be a barrier (a condom is preferred) in addition to one of the highly effective contraception methods described below during heterosexual activity.

Acceptable methods of highly effective contraception methods with a failure rate of less than 1% per year are‡:

- Combined estrogen- and progestogen-containing hormonal contraception associated with inhibition of ovulation given PO, intravaginally, or transdermally
- Progestin-only hormonal contraception associated with inhibition of ovulation given PO, by injection, or by implant

- Intrauterine device (IUD)
- Intrauterine hormone-releasing system (IUS)
- Bilateral tubal occlusion or ligation
- Vasectomized partner

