† In the context of this protocol, sexual abstinence is considered a highly effective method only if defined as refraining from heterosexual intercourse during the entire period specified above. Periodic abstinence (calendar, symptothermal, post-ovulation methods) and withdrawal (coitus interruptus) are not acceptable methods of contraception. The reliability of sexual abstinence needs to be evaluated in relation to the duration of the clinical trial and the preferred and usual lifestyle of the subject.

‡ If a contraceptive method listed above is restricted by local regulations/guidelines, then it does not qualify as an acceptable method of contraception for subjects participating at sites in this country/region.

Collection of Pregnancy Information

Male Patients With Partners Who Become Pregnant

- The Investigator will attempt to collect pregnancy information on any male patient's female partner who becomes pregnant while the male patient is in this study. This applies only to male patients who receive DAY101.
- After obtaining the necessary signed informed consent from the pregnant female partner directly, the Investigator will record pregnancy information on the appropriate form and submit it to the Sponsor within 24 hours of learning of the partner's pregnancy. The female partner will also be followed to determine the outcome of the pregnancy. Information on the status of the mother and child will be forwarded to the Sponsor. Generally, the follow-up will be no longer than 6 months following the estimated delivery date. Any termination of the pregnancy will be reported regardless of fetal status (presence or absence of anomalies) or indication for the procedure.

Female Patients Who Become Pregnant

The Investigator will collect pregnancy information on any female patient who becomes pregnant while participating in this study. The initial information will be recorded on the appropriate form and submitted to the Sponsor within 24 hours of learning of the patient's pregnancy.

The patient will be followed to determine the outcome of the pregnancy. The Investigator will collect follow-up information on the patient and the neonate, and the information will be forwarded to the Sponsor. Generally, follow-up will not be required for longer than 6 months beyond the estimated delivery date. Any termination of pregnancy will be reported, regardless of fetal status (presence or absence of anomalies) or indication for the procedure.

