### **2.2.1. End of Study and Length of Study**

The end of study is expected to occur 25 months after the last patient is enrolled. In addition, the Sponsor may decide to terminate this study at any time.

The total length of this study, from screening of the first patient to the end of study, is expected to be approximately 4 years.

On 03NOV2023, the sponsor announced the early termination of this study due to a change in clinical development priorities. As a result, all patients who have not ended the study will end study after being followed for at least 6 months after the first dose of the study drug. The originally planned interim analysis and primary analysis will not be performed. Instead, the final analysis will be conducted after all patients have ended the study and the data have been cleaned and finalized.

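### Protocol 8.1.1, 8.1.5 and Appendix F time the pregnancy-related windows from different points, so a pregnancy after study exit can fall inside the contraception period but outside collection, or under conflicting instructions

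*Protocol*

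**What the plan says.** Four rules bear on the same question.

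- **Collection, Protocol 8.1.5.** Details are gathered for pregnancies from the start of treatment "until 6 months after completing DAY101". The closing paragraph adds monitoring for cases "that occur after the last dose of DAY101 through 6 months for female patients and for 6 months for female partners of male patients", and makes this additional to reporting every pregnancy during the study. The combination partner appears in the section heading but in neither window. For procedures, the section refers sites to Appendix F.
- **Contraception, Appendix F.** The obligation covers the treatment period and continues "for 180 days after the last dose of study drug(s", so it counts any partner drug as well as DAY101.
- **Collection, Appendix F.** Information is collected on "any female patient who becomes pregnant while participating in this study", and on a male patient's partner only while he is in the study. The appendix also says that investigators need not actively look for pregnancy-related serious events in former patients.
- **Adverse events, Protocol 8.1.1.** These are reported "until 30 days after the last dose of DAY101 or combination partner, whichever was administered last". The master protocol therefore allows for a partner drug being the last one given.

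On study exit, Protocol 6.26 keeps patients in long-term follow-up, with contact about every 3 months, until consent is withdrawn, contact is lost, the patient dies or the study closes. For sub-study 102a, SAP 2.2.1 says that patients still on study after the early termination "will end study after being followed for at least 6 months after the first dose of the study drug".

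**The concern.** A pregnancy window should match the period in which the protocol asks patients to avoid pregnancy. Here one collection rule is tied to DAY101 alone and the other to study participation, while the contraception rule is tied to the final dose of any study drug. These agree only when DAY101 is the last drug given and the patient stays in the study long enough.

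Section 8.1.5 itself says that there is no relevant clinical experience in pregnancy and that no animal reproductive studies have been done, so each report has value. Other parts of the protocol do little to catch a missed case. Appendix F says that pregnancy itself is not an adverse event, so the adverse-event rules do not pick it up. The contacts after progression described in 6.26 mention later anticancer therapy and survival, but not pregnancy. Sites could also apply different rules: 8.1.5 asks them to monitor for 6 months after DAY101, and the appendix it sends them to stops at study exit.

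**Working it through.** The plan gives no figure of its own to reproduce. The check compares windows.

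**Inputs**
- Contraception: 180 days after the final dose of any study drug (Appendix F).
- 8.1.5 window: 6 months after DAY101. SAP 3.1.2 sets six months at 182.625 days; calendar six-month spans run from 181 to 184 days.
- In-study pregnancies: always collected (8.1.5 and Appendix F).
- L, days from the last DAY101 dose to the last partner dose: not in the documents. Assumed range 0 to 365.
- E, days from the last DAY101 dose to study exit: not in the documents. A patient taking a partner drug under the protocol is in the study, so E ≥ L.

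**Step 1. Monotherapy (L = 0), 8.1.5.** Uncovered days = max(0, 180 − 182.625) = 0. With calendar months the window is 181 to 184 days, so the result is again 0.

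**Step 2. Combination, post-DAY101 window of 8.1.5 taken alone.** Uncovered days = max(0, L + 180 − 182.625).

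**Step 3. Combination, both collection rules together.** A day is uncovered only if it is after exit, after the 8.1.5 window and inside the contraception period. Uncovered days = max(0, L + 180 − max(182.625, E)). The worst case is exit at the last partner dose, E = L.

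| L (days) | Step 2: post-DAY101 window alone | Step 3: both rules, exit at last partner dose |
|---|---|---|
| 0 | 0 | 0 |
| 7 | 4.4 | 4.4 |
| 28 | 25.4 | 25.4 |
| 84 | 81.4 | 81.4 |
| 168 | 165.4 | 165.4 |
| 365 | 362.4 | 365 + 180 − 365 = 180 |

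In the last row, 365 − 182.625 = 182.4 of the 362.4 days are days on the partner drug. In-study reporting covers those, so they drop out in step 3. The step 3 gap cannot exceed 180 days, and it is 0 once the patient stays in the study for 180 days after the last partner dose (E ≥ L + 180).

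**Step 4. Monotherapy, Appendix F alone.** If the patient leaves x days after the last dose (x assumed), Appendix F leaves 180 − x days uncollected: 180 at x = 0, 150 at x = 30 (the length of the adverse-event window) and 90 at x = 90. Section 8.1.5 leaves 0 in each case. The two instructions therefore differ by up to the whole contraception period.

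**Step 5. Can step 4 occur in 102a?** SAP 2.2 continues dosing until progression, unacceptable toxicity, withdrawal or death. SAP 2.2.1 times closure from first dose. A patient still on treatment at closure can therefore leave the study near the last dose. The documents give no exit or last-dose dates, so this shows that it is possible and not how often it happens.

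**Step 6. After re-anchoring.** If collection runs 6 months from the last dose of whichever drug came last, regardless of study status, uncovered days = max(0, L + 180 − (L + 182.625)) = 0 for every L. With a 181-day span it is still 0.

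**The case against.** The best defence is that the sections work together. Section 8.1.5 sets the window, and Appendix F only describes how to report. On that reading monotherapy has no gap at all, and the appendix's statement about not actively seeking information concerns pregnancy-related serious events after the study, not pregnancies as such. This stands as far as 8.1.5 goes. It does not remove the conflict, because Appendix F states its own collection period and a site following it would stop at exit.

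The combination gap also depends on a lag that nobody can read from these documents. The 8.1.1 wording would fit a difference of a few days between two dosing schedules, and the combination sub-protocol may carry its own pregnancy rule. Both points stand, and they limit the claim to something that can happen under the master text.

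There is a backstop too: abnormal outcomes count as serious events (8.1.5), and a related serious event that the investigator learns of after discharge must be reported (8.1.1). It is passive and limited to related events, so it does not replace collection.

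A reader might infer that a patient who stops DAY101 and continues the partner leaves collection while still exposed. The text does not support this, because in-study reporting continues. Nor do the documents support calling early exit in 102a likely, since 6 months from first dose is a minimum and no dates are given.

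**Conclusion.** The point holds as an inconsistency that must be reconciled, with two limited consequences.

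(a) In combination sub-protocols, collection misses a pregnancy that meets three conditions at once: after study exit, more than 6 months after the last DAY101 dose, and within 180 days of the last partner dose. The uncovered stretch is 0 to 180 days per patient. This assumes that the partner can be given after DAY101 ends and that the sub-protocol, which was not available, adds no rule of its own.

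(b) For a patient who leaves soon after the last dose, 8.1.5 requires 6 months of collection and Appendix F requires none after exit. This includes 102a, where there is no gap under 8.1.5 and the fault is the contradiction.

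Two further inferences should be resisted. This trial is not shown to be the only source of reproductive safety data, because Protocol 1.2.2 describes other DAY101 studies still running. The sentence "This applies only to male patients who receive DAY101" does not need to go: every regimen here contains DAY101, so it mainly excludes men who were never dosed.

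The issue affects the completeness of safety data. It does not touch the response rate, its confidence interval or the sample size.

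**What to change.** In both places in 8.1.5, keep the 6 months but count them from the final dose of DAY101 or the combination partner, whichever came later, using the 8.1.1 wording.

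In Appendix F, replace the two phrases that tie collection to being in the study with a reference to the 8.1.5 window. State that it applies after study exit unless consent for follow-up has been withdrawn. Check the combination sub-protocol for a pregnancy rule of its own and align it.

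The contraception requirement and treatment rules stay as they are. The pregnancy form and the 24-hour reporting route already exist, so the cost is protocol wording and a few late contacts after study exit. Patients who withdraw consent for follow-up would remain uncovered, and that should be accepted openly.
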